16.1.3 Primary Implementation Outcome

**Table 13: Summary of Primary Implementation Outcome
by Evaluation Period**

Number	Baseline Evaluation Period (N=)	IF Evaluation Period (N=)	Total (N=)
Received ED-initiated BUP	N	N	N
Received referral for MAT	N	N	N
Received ED-initiated BUP with referral for ongoing MAT	N (XX.x%)	N (XX.x%)	N (XX.x%)

Table 14: Summary of Primary Implementation Outcome by Site and Evaluation Period

Number	Baseline Evaluation Period				IF Evaluation Period			
	MA Johns Hopkins ED (N=)	GNY Mount Sinai ED/Beth Israel (N=)	OV University of Cincinnati ED (N=)	PNW Harborview Med Center ED (N=)	MA Johns Hopkins ED (N=)	GNY Mount Sinai ED/Beth Israel (N=)	OV University of Cincinnati ED (N=)	PNW Harborview Med Center ED (N=)
Received ED-initiated BUP	N				N			
Received Referral for MAT	N				N			
Received ED-initiated BUP with Referral for Ongoing MAT	N (XX.x%)				N (XX.x%)			

Table 15: Analysis Results for Primary Implementation Outcome

GLMM		Bayesian Analysis		
Intervention Coefficient	p-value	Risk Difference Estimation Time Point	Risk Difference	95% Credible Interval
X.xx	x.xxx	Mid-point (day 632)	X.xx	X.xx; X.xx
		COVID-19 Pause (day 1423)	X.xx	X.xx; X.xx

**Table 16: Summary of Primary Implementation Outcome
by Sex and Evaluation Period**

Number	Baseline Evaluation Period		IF Evaluation Period	
	Male (N=)	Female (N=)	Male (N=)	Female (N=)
Received ED-initiated BUP	N		N	
Received Referral for MAT	N		N	
Received ED-initiated BUP with Referral for Ongoing MAT	N (XX.x%)		N (XX.x%)	

Table 17: Summary of Primary Implementation Outcome by Race and Evaluation Period

Number	Baseline Evaluation Period			IF Evaluation Period		
	White (N=)	Black/African American (N=)	Other (N=)	White (N=)	Black/African American(N=)	Other (N=)
Received ED-initiated BUP	N			N		
Received Referral for MAT	N			N		
Received ED-initiated BUP with Referral for Ongoing MAT	N (XX.x%)			N (XX.x%)		

**Table 18: Summary of Primary Implementation Outcome
by Ethnicity and Evaluation Period**

Number	Baseline Evaluation Period		IF Evaluation Period	
	Hispanic or Latino (N=)	Not Hispanic or Latino (N=)	Hispanic or Latino (N=)	Not Hispanic or Latino (N=)
Received ED-initiated BUP	N		N	
Received Referral for MAT	N		N	
Received ED-initiated BUP with Referral for Ongoing MAT	N (XX.x%)		N (XX.x%)	

**Table 19: Final Covariate Adjusted Model Analysis Results
for Primary Implementation Outcome**

Covariate ¹	N	Coefficient	95% Credible Interval
Study Phase			
BEP	N	[ref]	[ref]
IFEP	N	X.x	X.xx; X.xx
Sex			
Male	N	[ref]	[ref]
Female	N		
Race			
White	N	[ref]	[ref]
Black/African American	N		
Other	N		
Ethnicity			
Not Hispanic/Latino	N	[ref]	[ref]
Hispanic/Latino	N		
Sex-by-study phase interaction ²			
Male	N	X.x	X.xx; X.xx
Female	N	X.x	X.xx; X.xx
Race-by-study phase interaction ²			
White	N	X.x	X.xx; X.xx
Black	N	X.x	X.xx; X.xx
Other	N	X.x	X.xx; X.xx
Ethnicity-by-study phase interaction ²			
Not Hispanic/Latino	N	X.x	X.xx; X.xx
Hispanic/Latino	N	X.x	X.xx; X.xx

¹ Note that only covariates which remained in the final covariate-adjusted model will be included in this table.

² Coefficient and corresponding credible intervals are presented for the intervention effect in a particular subgroup (e.g., males).

Table 20: Summary of MOUD Practices by Site Over Time from EHR-abstracted Data

	Baseline Evaluation Period					IF Evaluation Period				
	MA Johns Hopkins ED	GNY Mount Sinai ED	OV University of Cincinnati ED	PNW Harborview Medical Center ED	Total	MA Johns Hopkins ED	GNY Mount Sinai ED	OV University of Cincinnati ED	PNW Harborview Medical Center ED	Total
Buprenorphine										
Administered	N									
Prescribed	N									
Administered and prescribed	N									
Unique providers administering or prescribing	N									
Naloxone										
Dispensed	N									
Prescribed	N									
Dispensed and prescribed	N									
Unique providers dispensing or prescribing	N									
X-waiver										
Physicians	N									
APPs	N									
Additional staff (counselors/peers)	N									

Table 21: COVID-19 Sensitivity Analyses Results for Primary Implementation Outcome

Sensitivity Analysis	GLMM		Bayesian Analysis		
	Intervention Coefficient	p-value	Risk Difference Estimation Time Point	Risk Difference	95% Credible Interval
Pre-COVID data	X.xx	x.xxx	Mid-point (day 632)	X.xx	X.xx; X.xx
			COVID-19 Pause (day 1423)	X.xx	X.xx; X.xx
COVID pause removed	X.xx	x.xxx	Mid-point (day 632)	X.xx	X.xx; X.xx
			COVID-19 Pause (day 1423)	X.xx	X.xx; X.xx

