7.2 Analysis of the Primary Implementation Outcome Measure

For the primary implementation outcome measure, a Generalized Linear Mixed Model will be used to compare the rates of provision of ED-initiated BUP with referral for ongoing MAT between the baseline and IF evaluation periods. The model for the primary analysis will be used to compare the rates of ED-initiated BUP with referral for ongoing MAT between the IFEP and the BEP is:

$$\text{logit}(p_{si}) = \alpha + \beta t_{si} + \gamma f_{si} + r_s$$

where

- p_{si} is the probability of success of patient participant i at site s ,
- t_{si} is the calendar time of enrollment of patient participant i at site s ,
- f_{si} is the indicator of whether patient participant i at site s is in the BEP ($f_{si}=0$) or IFEP ($f_{si}=1$), and
- r_s is the random effect of site s , where $r_s \sim N(0, \sigma^2)$.

In this model the γ estimate represents the estimated difference in the logit of the probability of success and captures the effect of implementation facilitation. Note that calendar time is measured in days and defined in Section 3.3.6. The model will test a one-tailed hypothesis at the 0.05 level. The null and alternative hypotheses are:

$$H_0: \gamma \leq 0$$

$$H_a: \gamma > 0.$$

The following SAS code fragment estimates this model:

```
proc glimmix data = primout method = quad;
  class arm (ref="1") site;
  model z = arm time / dist = binomial link = logit solution;
  random intercept / subject = site;
  estimate "trt effect" arm 1 -1 / cl;
  lsmeans arm / cl ilink;
run;
```

where

- primout is the dataset containing the variables required for the primary outcome analyses;
- arm is 1 for the BEP and 2 for the IFEP;
- z is an indicator of the ED-initiated BUP (primary implementation outcome measure); and

- time is defined in Section 3.3.6.

The main focus for estimation is the estimated Risk Difference (RD) defined as the difference between IFEP and BEP success rates, ($p_{IFEP} - p_{EP}$) with its 95% credible interval (CI). The estimated RD and its 95% CI will be obtained using the Bayesian approach outlined in the protocol Appendix 19.0 and in this SAP. Below is the SAS code used for analyzing the primary implementation outcome for this model:

```
proc mcmc data = simmsimul nbi = 1000 nmc = 10000 thin = 2 seed = 159  
monitor =(alpha-gammacoeff gammacoeff_gt_0 p1 p2 pdiff) statistics = (summary  
intervals);  
  parms alpha-gammacoeff 0;  
  parms sigma2 1;  

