  prior alpha-gammacoeff~normal(mean = 0, var = 1000);  
  prior sigma2~ igamma(shape = 0.001, scale = 0.001)  
  random b0 ~ normal(mean = 0, var = sigma2) subject = site;  
  array p[2];  
  p[treat+1] = logistic(alpha + beta * 22 + gammacoeff * treat);  
  pdiff = p2 - p1;  
  eta = alpha + beta * time + gammacoeff * treat + b0;  
  pi = logistic(eta);  
  model z ~ binomial(n = trials, p = pi);  
  gammacoeff_gt_0 = gammacoeff > 0;  
run;
```

where

- simmsimul is the analytic dataset (e.g., simulated dataset in power calculations);
- alpha is the intercept, beta is the coefficient β , gammacoeff is γ and sigma2 is the variance of the random effect of site from the logistic regression model above;
- time is defined in Section 3.3.6;
- treat is equal to '0' for the BEP and '1' for the IFEP;
- p1 is the proportion of success during the BEP;
- p2 is the proportion of successes in the IFEP; and
- pdiff is the risk difference.

The primary implementation outcome will be summarized by site and evaluation period with frequencies and percentages. Results of the Bayesian approach, that is the model specified above, will be presented tabularly with estimates and 95% credible intervals for the risk difference.

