16.1.4 Primary Effectiveness Outcome

Table 22: Summary of Primary Effectiveness Outcome by Evaluation Period

Number	Baseline Evaluation Period (N=)	IF Evaluation Period (N=)
Self-report Treatment Engagement	N	N
Facility confirmed Treatment Engagement	N	N
Missing primary effectiveness outcome (i.e., to be imputed as non-engaged)	N	N
Engagement in formal addiction treatment for OUD at Day 30	N (XX.x%)	N (XX.x%)

Table 23: Summary of Primary Effectiveness Outcome by Site and Evaluation Period

Number	Baseline Evaluation Period				IF Evaluation Period			
	MA Johns Hopkins ED (N=)	GNY Mount Sinai ED/Beth Israel (N=)	OV University of Cincinnati ED (N=)	PNW Harborview Med Center ED (N=)	MA Johns Hopkins ED (N=)	GNY Mount Sinai ED/Beth Israel (N=)	OV University of Cincinnati ED (N=)	PNW Harborview Med Center ED (N=)
Self-report Treatment Engagement	N				N			
Facility confirmed Treatment Engagement	N				N			
Missing primary effectiveness outcome (i.e., to be imputed as non-engaged)	N				N			
Engagement in formal addiction treatment for OUD at Day 30	N (XX.x%)				N (XX.x%)			

Table 24: Analysis Results for Primary Effectiveness Outcome				
GLMM		Bayesian Analysis		
Intervention Effect Coefficient	p-value	Risk Difference Estimation Time Point	Risk Difference	95% Credible Interval
X.xx	x.XXX	Mid-point (time = 632)	X.xx	X.xx; X.xx
		COVID-19 Pause (time = 1423)	X.xx	X.xx; X.xx

Table 25: Summary of Primary Effectiveness Outcome by Sex and Evaluation Period

Number	Baseline Evaluation Period		IF Evaluation Period	
	Male (N=)	Female (N=)	Male (N=)	Female (N=)
Self-report Treatment Engagement	N		N	
Facility confirmed Treatment Engagement	N		N	
Missing primary effectiveness outcome (i.e., to be imputed as non-engaged)	N		N	
Engagement in formal addiction treatment for OUD at Day 30	N (XX.x%)		N (XX.x%)	

Table 26: Summary of Primary Effectiveness Outcome by Race and Evaluation Period

Number	Baseline Evaluation Period			IF Evaluation Period		
	White (N=)	Black/African American (N=)	Other (N=)	White (N=)	Black/African American (N=)	Other (N=)
Self-report Treatment Engagement	N			N		
Facility confirmed Treatment Engagement	N			N		
Missing primary effectiveness outcome (i.e., to be imputed as non-engaged)	N			N		
Engagement in formal addiction treatment for OUD at Day 30	N (XX.x%)			N (XX.x%)		

**Table 27: Summary of Primary Effectiveness Outcome
by Ethnicity and Evaluation Period**

Number	Baseline Evaluation Period		IF Evaluation Period	

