Evaluation of the distributional properties of the time variable data indicated that this variable, originally included as one of the explanatory factors in the analytical model, overlaps 96% with the intervention/treatment factor in the study. Including two highly overlapping variables in the analytical model can create a computational, statistical, and mathematical error. Collinearity, or high association between two explanatory variables means that the collinear variables contain the same information about the dependent variable, and that these only nominally different measures actually quantify the same

phenomenon or information. In CTN-0069, the variables “time” and “arm” are highly redundant. The best and most statistically robust analytical models are called “low noise” models in which the predictor variables each correlate highly with the outcome variable but correlate with each other at most only minimally. Collinearity and redundancy may lead to a failure to reject a false null hypothesis of no intervention effect. Consequently, the “time” variable was removed from the adjusted computational model.

Site. Additionally, the four geographically diverse study sites were purposefully selected to represent different clinical contexts and different patient populations. Conceptually, these EDs cannot be considered as a random sample of all EDs in the US, and probabilistically, no four values selected from a large population can be considered to represent randomness, even if they are drawn by chance. Consequently, site was included in the primary analytic models as a fixed effect, and not a random one in order to provide additional information on between site differences. The study results demonstrated not only statistical difference effects between the sites, but also substantial, large, important, and informative site differences.

Thus, the final analytic model for both the primary implementation and effectiveness outcomes was a logistic regression model with fixed effects for site and evaluation period.

Site Differences for Primary Effectiveness Outcome

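### The Revised SAP drops time from the primary model without saying how the risk difference, the stated main estimate, is then obtained; the second evaluation day in the results tables is also wrong

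*SAP*

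**What the plan says.** SAP 7.2 states: "The main focus for estimation is the estimated Risk Difference (RD) defined as the difference between IFEP and BEP success rates". It also names the source: "The estimated RD and its 95% CI will be obtained using the Bayesian approach outlined in the protocol Appendix 19.0 and in this SAP". The code there has a linear time term and a random site intercept, "eta = alpha + beta * time + gammacoeff * treat + b0", and computes the two probabilities at a fixed time value: "p[treat+1] = logistic(alpha + beta * 22 + gammacoeff * treat".

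SAP 7.2.1 takes the p-value from the logistic mixed model of Section 7.2, under the ChangeToOne policy, and the risk difference from the Bayesian fit. Because time is linear on the log-odds scale, the risk difference changes over time, so it is to be estimated at 01/01/2019 and 03/02/2020. Table 15 (implementation) and Table 24 (effectiveness) therefore show one coefficient and p-value beside two risk-difference rows, under a column headed "Risk Difference Estimation Time Point", the first in Table 24 labelled "Mid-point (time = 632)" and the second at 1423. Tables 21 and 29 repeat the layout for the COVID-19 sensitivity analyses.

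The Revised SAP, appended after SAP 18.6, removes time as collinear with period and makes site a fixed effect. It concludes that "the final analytic model for both the primary implementation and effectiveness outcomes was a logistic regression model with fixed effects for site and evaluation period". It says nothing about the risk difference, the MCMC code, the two dates or the table shells.

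**The concern.** In the SAP body the p-value and the risk difference came from two procedures with the same linear predictor (time, period, random site), so both described one time-adjusted effect. The Revised SAP breaks that link without saying what replaces it. Someone filling the tables as laid out has two routes. One keeps the MCMC model for the risk difference and changes only the p-value model. The table then sets a period effect not adjusted for calendar time beside one that is, and the reader cannot tell that the two answer different questions. The other drops time from both, and the reason for two dates disappears.

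At stake is the main estimate of both primary outcomes: how it is defined, and whether it agrees with the test beside it. This is a separate question from whether dropping time was justified.

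**Working it through.** **1. Reproduce the evaluation days.** The origin is the first site's opening, 4/10/2017 (SAP 3.3.6), counted as day 1.
- 01/01/2019: 365 + 266 = 631 days later, so day 632. This matches the tables.
- 03/02/2020: 631 + 365 + 61 = 1057 days later, so day 1058. The tables print 1423, and 1423 - 1058 = 365, so the printed day is exactly 365 days late (03/02/2021).
- Last enrolment, 10/4/2020: 1057 + 216 = 1273 days later, so day 1274. Day 1423 is 149 days after that.
- SAP 3.3.6 defines time from each site's own opening. On that clock no patient exceeds 1006 days, so 1423 is not rescued. It also means that 632 uses a different origin from the defined variable.
- The code evaluates at 22. The protocol's code measures time in months, with an average near month 22 (Protocol 12.8.1). In the SAP time is in days, so 22 is a date in the first site's opening month.

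**2. What the evaluation day does.** RD(t) = expit(a + b(t - 632) + g) - expit(a + b(t - 632)), set to 5% vs 25% at day 632 (rates from Protocol Table 4). The secular odds ratio per year is an assumption, since the documents give none.

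| Odds ratio per year | t = 22 | 632 | 1058 | 1423 |
|---|---|---|---|---|
| 0.8 | 0.255 | 0.200 | 0.165 | 0.139 |
| 1.0 (no time term) | 0.200 | 0.200 | 0.200 | 0.200 |
| 1.25 | 0.152 | 0.200 | 0.238 | 0.272 |
| 1.5 | 0.119 | 0.200 | 0.271 | 0.333 |
| 2.0 | 0.079 | 0.200 | 0.322 | 0.408 |

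Without a time term, b = 0 and both date rows hold one number (apart from Monte Carlo error). With a time term, the wrong day changes the answer.

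**3. If only the p-value model changes.** Simulation used the SAP 3.3.6 dates, 120 patients per site-period and no secular trend. Delta-method intervals stood in for diffuse-prior credible intervals. Ranges run from a common to a fixed site intercept in the time-adjusted model.

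| Rates | 95% half-width, final model | 95% half-width, time-adjusted, day 632 | p<0.05 beside an interval covering 0 |
|---|---|---|---|
| 15% vs 25% | 5.0 points | 10.0-13.0 | about 50-66% |
| 25% vs 40% | 5.8 | 11.8-15.2 | about 30-55% |
| 5% vs 25% | 4.3 | 8.2-10.5 | 0.3-4% |

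**4. Hand check.** Final model, 480 per period, 15% vs 25%: SE = sqrt((0.15×0.85 + 0.25×0.75)/480) = 0.0256, and 1.96 × 0.0256 = 5.0 points. One-sided 5% power is 0.988, so the p-value is almost always significant and the conflict rate is close to the chance that the wider interval covers zero. With half-width h and true difference D, that chance is Φ(1.96 - 1.96D/h).
- 15% vs 25%, D = 10: Φ(0) = 0.50 at h = 10.0; Φ(0.45) = 0.67 at h = 13.0.
- 25% vs 40%, D = 15: Φ(-0.53) = 0.30 at h = 11.8; Φ(0.03) = 0.51 at h = 15.2.
- 5% vs 25%, D = 20: Φ(-2.82) = 0.002 at h = 8.2; Φ(-1.77) = 0.04 at h = 10.5.

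These agree with the simulation to within a few percentage points.

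**5. Baseline for comparison.** A one-sided 5% test beside a two-sided 95% interval disagrees at times even within one model: Φ(1.96 - 1.96D/h) - Φ(1.645 - 1.96D/h). In the time-adjusted model this is 0.12 at both half-widths for 15% vs 25%, and 0.10 to 0.12 for 25% vs 40%. Simulation gives roughly 10-13% in these two scenarios.

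**The case against.** Several objections have force.

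- **The two routes are not the only ones.** The SAP body governs tables for the final study report, while the Revised SAP is retrospective and refers to the manuscript. The report's tables may follow the SAP body throughout, with time in both p-value and risk difference, and the addendum may document only the manuscript's model. Or the Bayesian columns may have been dropped. This stands. The documents do not say which happened, so a reader must not infer that a mismatched table was produced. The gap remains: if the columns were dropped, no method for the stated main estimate is given.
- **The consistent route is the more natural one.** The addendum speaks of a single final model for both outcomes, and carrying it into the MCMC fit leaves only a redundant row. That is fair. The 50-66% figure belongs to the other route and is not a general consequence of the addendum.
- **Part of the disagreement was already in the plan**, because a one-sided test sits beside a two-sided interval. That part is roughly 10-13% in the first two scenarios and should be read off first. Protocol 12.8 itself places 15% vs 25% and 25% vs 40% below 80% power; at 5% vs 25% conflict is rare.
- **A logistic model with site and period does give a risk difference.** Correct: it follows from the fitted probabilities. One might read the addendum as leaving the risk difference unobtainable, but what is missing is a stated derivation and an interval method.

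**Conclusion.** The concern holds as a gap in specification, with one plain error. The Revised SAP changes the primary model and leaves the derivation of the main estimate unstated. Completed as laid out, Tables 15, 24, 21 and 29 would either pair a time-unadjusted p-value with a time-adjusted risk difference or print one number twice.

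The conflict rates apply to the first case only. They assume no secular trend, equal enrolment of 120 per site-period, and delta-method intervals in place of credible intervals. A real trend would also separate the point estimates systematically.

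The day-1423 error rests on date arithmetic alone. The printed day is not the date that SAP 7.2.1 names, and under a time model that row would extrapolate beyond enrolment. The value 22 in the code, with time in days, needs correcting for the same reason.

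The documents do not show that any published estimate is wrong. The change should be made because the main estimate ought to be reproducible from the stated final model.

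**What to change.** In the Revised SAP, state that the risk difference comes from the final site-plus-period logistic model: predict each enrolled patient's probability under each period at that patient's own site, average the differences over all enrolled patients at the four sites, and give a 95% interval. The interval can be delta-method, or a credible interval from refitting the MCMC with fixed site and no time, which keeps the interval type in SAP 7.2.

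In Tables 15 and 24, replace the two date rows with this single estimate. Keep the prespecified time-adjusted model as a separately labelled row with its own p-value and its own risk difference at day 632, and at day 1058 if the second date is kept. Set the evaluation time in the code to match, and state one time origin for both the variable and the evaluation day. Do not pair the p-value of one model with the risk difference of the other. Use the same layout in Tables 21 and 29.

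The cost is revised wording, four table shells and a few lines of code. No new data are needed.

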16.1.4 Primary Effectiveness Outcome

Table 22: Summary of Primary Effectiveness Outcome by Evaluation Period

Number	Baseline Evaluation Period (N=)	IF Evaluation Period (N=)
Self-report Treatment Engagement	N	N
Facility confirmed Treatment Engagement	N	N
Missing primary effectiveness outcome (i.e., to be imputed as non-engaged)	N	N
Engagement in formal addiction treatment for OUD at Day 30	N (XX.x%)	N (XX.x%)

Table 23: Summary of Primary Effectiveness Outcome by Site and Evaluation Period

Number	Baseline Evaluation Period				IF Evaluation Period			
	MA Johns Hopkins ED (N=)	GNY Mount Sinai ED/Beth Israel (N=)	OV University of Cincinnati ED (N=)	PNW Harborview Med Center ED (N=)	MA Johns Hopkins ED (N=)	GNY Mount Sinai ED/Beth Israel (N=)	OV University of Cincinnati ED (N=)	PNW Harborview Med Center ED (N=)
Self-report Treatment Engagement	N				N			
Facility confirmed Treatment Engagement	N				N			
Missing primary effectiveness outcome (i.e., to be imputed as non-engaged)	N				N			
Engagement in formal addiction treatment for OUD at Day 30	N (XX.x%)				N (XX.x%)			

Table 24: Analysis Results for Primary Effectiveness Outcome				
GLMM		Bayesian Analysis		
Intervention Effect Coefficient	p-value	Risk Difference Estimation Time Point	Risk Difference	95% Credible Interval
X.xx	x.XXX	Mid-point (time = 632)	X.xx	X.xx; X.xx
		COVID-19 Pause (time = 1423)	X.xx	X.xx; X.xx

Table 25: Summary of Primary Effectiveness Outcome by Sex and Evaluation Period

Number	Baseline Evaluation Period		IF Evaluation Period	
	Male (N=)	Female (N=)	Male (N=)	Female (N=)
Self-report Treatment Engagement	N		N	
Facility confirmed Treatment Engagement	N		N	
Missing primary effectiveness outcome (i.e., to be imputed as non-engaged)	N		N	
Engagement in formal addiction treatment for OUD at Day 30	N (XX.x%)		N (XX.x%)	

Table 26: Summary of Primary Effectiveness Outcome by Race and Evaluation Period

Number	Baseline Evaluation Period			IF Evaluation Period		
	White (N=)	Black/African American (N=)	Other (N=)	White (N=)	Black/African American (N=)	Other (N=)
Self-report Treatment Engagement	N			N		
Facility confirmed Treatment Engagement	N			N		
Missing primary effectiveness outcome (i.e., to be imputed as non-engaged)	N			N		
Engagement in formal addiction treatment for OUD at Day 30	N (XX.x%)			N (XX.x%)		

**Table 27: Summary of Primary Effectiveness Outcome
by Ethnicity and Evaluation Period**

Number	Baseline Evaluation Period		IF Evaluation Period	
	Hispanic or Latino (N=)	Not Hispanic or Latino (N=)	Hispanic or Latino (N=)	Not Hispanic or Latino (N=)
Self-report Treatment Engagement	N	N		
Facility confirmed Treatment Engagement	N	N		
Missing primary effectiveness outcome (i.e., to be imputed as non-engaged)	N	N		
Engagement in formal addiction treatment for OUD at Day 30	N (XX.x%)	N (XX.x%)		

**Table 28: Final Covariate Adjusted Model Analysis Results
for Primary Effectiveness Outcome**

Covariate ¹	N	Coefficient	95% Credible Interval
Study Phase			
BEP	N	[ref]	[ref]
IFEP	N	X.x	X.xx; X.xx
Sex			
Male	N	[ref]	[ref]
Female	N	X.x	X.xx; X.xx
Race			
White	N	[ref]	[ref]
Black	N	X.x	X.xx; X.xx
Other	N	X.x	X.xx; X.xx
Ethnicity			
Not Hispanic/Latino		[ref]	[ref]
Hispanic/Latino		X.x	X.xx; X.xx
Sex-by-study phase interaction ²			
Male	N	X.x	X.xx; X.xx
Female	N	X.x	X.xx; X.xx
Race-by-study phase interaction ²			
White	N	X.x	X.xx; X.xx
Black	N	X.x	X.xx; X.xx
Other	N	X.x	X.xx; X.xx
Ethnicity-by-study phase interaction ²			
Not Hispanic/Latino	N	X.x	X.xx; X.xx
Hispanic/Latino	N	X.x	X.xx; X.xx

¹ Note that only covariates which remained in the final covariate-adjusted model will be included in this table.

² Coefficient and corresponding credible intervals are presented for the intervention effect in a particular subgroup (e.g., males).

Table 29: COVID-19 Sensitivity Analyses Results for Primary Effectiveness Outcome

Sensitivity Analysis	GLMM		Bayesian Analysis		
	Intervention Coefficient	p-value	Risk Difference Estimation Time Point	Risk Difference	95% Credible Interval
Pre-COVID data	X.xx	x.XXX	Mid-point (day 632)	X.xx	X.xx; X.xx
			COVID-19 Pause (day 1423)	X.xx	X.xx; X.xx
COVID pause removed	X.xx	x.XXX	Mid-point (day 632)	X.xx	X.xx; X.xx
			COVID-19 Pause (day 1423)	X.xx	X.xx; X.xx

Table 30: Summary of Treatment Engagement at Day 30 during the IF Evaluation Period by ED-initiated BUP Status: All Patient-participants (Missing Engagement Status Imputed as Not Engaged)

ED-initiated BUP Status	Pre-IF Cohort (N =)	Post-IF Cohort (N =)
No	N (XX.x%)	N (XX.x%)
Yes	N (XX.x%)	N (XX.x%)

Table 31: Summary of Treatment Engagement at Day 30 during the IF Evaluation Period by ED-initiated BUP Status: Patient-participants with Non-missing Engagement Status (No Imputation)

ED-initiated BUP Status	Pre-IF Cohort (N =)	Post-IF Cohort (N =)
No	N (XX.x%)	N (XX.x%)
Yes	N (XX.x%)	N (XX.x%)

Table 32: Analysis of Treatment Engagement at Day 30 during the IF Evaluation Period by ED-initiated BUP Status

Method of Handling Missing Data	N	p-value
Missing engagement status imputed as not engaged)	N	X.xxx
No Imputation (i.e., complete case)	N	X.xxx

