7.5 Supportive Analyses of the Primary Outcome Measures

7.5.1 Subgroup Analyses

The NIH requires subgroup analyses by sex, race, and ethnicity (NIH, 2016). Analyses will be conducted by evaluation period. Primary implementation and effectiveness outcomes will also be summarized by these subgroups and evaluation period.

Several covariates may influence the primary implementation and effectiveness outcome measures. The GLMM models proposed for the primary outcomes will be expanded to adjust for potential effect modifiers. The models will be adjusted for sex, race, and ethnicity as well as each of their interactions with treatment. Below is a mathematical formulation of the models:

$$\begin{aligned} \text{logit}(p_{si}) = & \alpha + \beta t_{si} + \gamma f_{si} + \theta_1 \text{sex}_{si} + \theta_2 \text{race}_{si} + \theta_3 \text{ethnicity}_{si} \\ & + \theta_4 f_{si} * \text{sex}_{si} + \theta_5 f_{si} * \text{race}_{si} + \theta_6 f_{si} * \text{ethnicity}_{si} + r_s \end{aligned}$$

where sex, race, and ethnicity are indicators for their respective variables. They will be entered into the model in a stepwise manner using a p-value cutoff of 0.05. Note that an interaction term will always be included with its corresponding main effects, and the effect of treatment period will be forced into the model. If there are convergence issues, the model will be fit with each demographic factor separately. A forest plot will summarize the estimated risk difference from models where each demographic factor is considered separately to evaluate potential in trends in effect modification, which may not be statistically significant at the 0.05 level.

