As noted in the manuscript, there were substantial site differences with respect to the primary effectiveness outcome. Three of the four sites was associated with an increase in treatment engagement during the IF evaluation period, however for one site there was a decrease. To explore this further, a logistic regression model was fit assessing the site-by-evaluation period interaction. In this model, there was a statistically significant interaction ($p=0.021$) indicating that the differences observed across sites was statistically significant. Future work could explore these relationships further, including evaluation of differences in site characteristics that may explain the observed qualitative interaction.

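### For the effectiveness outcome, the subgroup model has no site-by-period terms, so the reported difference in IF effect between sites can appear as race or ethnicity effect modification in Table 28 and the forest plot

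*SAP*

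**What the plan says.** SAP 7.5.1 extends the primary model to sex, race and ethnicity: "The models will be adjusted for sex, race, and ethnicity as well as each of their interactions with treatment". The only site term in the formula is the intercept r_s, coded in SAP 7.2 as "random intercept / subject = site". No term lets the period effect vary by site. On selection, 7.5.1 says "They will be entered into the model in a stepwise manner using a p-value cutoff of 0.05", and the first footnote to Table 28 adds "Note that only covariates which remained in the final covariate-adjusted model will be included in this table". The second footnote says what the interaction rows show: "Coefficient and corresponding credible intervals are presented for the intervention effect in a particular subgroup (e.g., males". Section 7.5.1 also plans a forest plot of risk differences from one-factor models, which is not limited to significant terms.

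The Revised SAP makes site a fixed main effect and drops time from the primary model. It says the four EDs were "purposefully selected to represent different clinical contexts and different patient populations". For the primary effectiveness outcome, "a logistic regression model was fit assessing the site-by-evaluation period interaction", with p=0.021: engagement rose at three sites and fell at one. The Revised SAP does not restate the 7.5.1 model or say which model produced Table 28.

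**The concern.** A site intercept adjusts for sites having different engagement levels. It does not adjust for sites having different IF effects. Suppose the period effect truly varies by site, and a race or ethnicity group is over-represented where the effect is reversed. With site-by-period omitted, race-by-period is then the term left to pick up some of that variation. The group looks as if it benefits less, even when race makes no difference within any ED.

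These are the subgroup results that the SAP says the NIH requires. A poor result at one ED could be read as IF working less well for a racial or ethnic group, or a real subgroup difference could be masked. The 0.05 cutoff gives limited protection, because the p-value that decides retention is affected by the same bias. The forest plot has no cutoff at all.

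**Working it through.** **The plan's own figure.** p=0.021 cannot be reproduced, because the documents give no counts by site and period. With four sites the interaction has 3 df, and p=0.021 corresponds to chi-square 9.73. That value calibrates the runs below.

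**Inputs from the documents.** 240 patients per site, so 120 per site-period (SAP 10.0); 25% baseline engagement and 40–50% under IF (Protocol 12.5).

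**Assumptions.** Race is binary. Race has no effect on the IF effect within any site. Race shares by site are assumed, because none are given (Table 12 is an empty shell). Models use fixed site intercepts and no time term; tests are two-sided at 5%.

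**Direction and rough size by hand.** The spurious race-by-period log-OR is roughly the mean site effect in group 1 minus that in group 0. Take IF rates of 40% at three sites and 21.3% at the fourth.
- Site log-ORs: logit(0.40) − logit(0.25) = +0.693; logit(0.213) − logit(0.25) = −0.208.
- Let group 1 be 20% of patients at three sites and 60% at the fourth.
- Group 1 mean: (3×0.2×0.693 − 0.6×0.208)/1.2 = 0.243.
- Group 0 mean: (3×0.8×0.693 − 0.4×0.208)/2.8 = 0.564.
- Difference: −0.32. The fitted model gives −0.30 (ratio of ORs 0.74).

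**Run A (shares graded across sites).** Site log-ORs +0.6, +0.5, +0.4 and −0.4 from 25% give IF rates of 37.8%, 35.5%, 33.2% and 18.3%.
- Weight per site: w = 1/[1/(120×0.25×0.75) + 1/(120·p·(1−p))] = 12.52, 12.37, 12.19, 9.97.
- Weighted mean log-OR: 0.310.
- Noncentrality: Σw(log-OR − 0.310)² = 1.05 + 0.45 + 0.10 + 5.03 = 6.6.
- Expected chi-square: 3 + 6.6 = 9.6, against 9.73.

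Without site-by-period (bias and ratio of ORs are for the ordering with the highest share at the reversed site):

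| Share range | Bias (log-OR) | Ratio of ORs | Rejects, highest share at reversed site | Rejects, averaged over orderings | SE without → with the term |
|---|---|---|---|---|---|
| 30–50% | −0.11 | 0.89 | 6% | 6% | 0.301 → 0.306 (+2%) |
| 20–60% | −0.21 | 0.81 | 10% | 7% | 0.304 → 0.321 (+6%) |
| 10–80% | −0.41 | 0.67 | 26% | 12% | 0.306 → 0.366 (+20%) |

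With site-by-period, bias is about 0 and rejection about 5% in every row. With equal shares, both models reject in about 5%. (2,000 replicates per scenario; 24 orderings × 300 for the averages. Ratios were taken before rounding the log-OR.)

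**Run B (three sites share one mix, the fourth differs).** 40% at three sites and 21.3% at the fourth give noncentrality 6.73 = 9.73 − 3. 4,000 replicates.

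| Share, three sites vs fourth | Ratio of ORs | Rejects without the term | Rejects with the term |
|---|---|---|---|
| 30% vs 30% | 1.00 | 5.2% | 5.2% |
| 20% vs 40% | 0.85 | 8.3% | 5.3% |
| 20% vs 60% | 0.74 | 15.1% | 4.8% |
| 20% vs 80% | 0.66 | 27.2% | 5.4% |
| 10% vs 90% | 0.54 | 47.9% | 5.4% |

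Taking 9.73 itself as the noncentrality (fourth site at 18.1%) makes no allowance for chance and is an upper case: 8.6%, 20.7%, 36.1% and 63.0% for the four unequal mixes.

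**Run C.** A further simulation gave bias of about −0.07 to −0.34 and rejection of 5.5–22% without the term, against about 0 and 4–5% with it.

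**Implementation outcome.** With baseline levels of 2–15% across sites but one common period odds ratio, the model without the term rejects in 4.6–5.0%, even at 10% vs 90%. Differing levels alone cause no problem on the logit scale.

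**The case against.** The strongest objection is that the key ingredient is missing. The Revised SAP says patient populations differ but names neither race nor ethnicity, and equal shares give no bias. That stands, and it is why the conclusion is conditional. The 26% figure also needs the highest share at the one reversed site; averaging over orderings brings it down to 12%.

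Other points that stand:
- SAP 11.0 reports very low baseline-period recruitment at one site, fairly low at another, and two heading above target. The equal 120 per cell is therefore a convenience, and the bias depends on the reversed site's actual size.
- SAP 9.0 treats secondary findings as noteworthy only when p is well below 0.05, so the rejection rates are not rates of published claims.
- The site interaction came from exploration after results. Replacing a prespecified model on that basis would be data-driven, which favours a sensitivity analysis.

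A reader might infer that the same fault affects Table 19. The documents do not support that: p=0.021 concerns engagement only, and no site-by-period finding is given for BUP provision. A reader might also extend the point to sex, but nothing indicates that sex mix varies by site. Nor are the descriptive tables at fault. Table 26, "Summary of Primary Effectiveness Outcome by Race and Evaluation Period", and Tables 17, 18 and 27 show counts and percentages and claim no adjusted effect.

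What the objection leaves untouched is that the forest plot is unfiltered and that no listed shell crosses race or ethnicity with both site and period. A reader of the planned output could not tell a site difference from a subgroup difference.

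**Conclusion.** The point holds for the effectiveness outcome, in Table 28 and the forest plot, for race and ethnicity. The model omits a source of variation that the Revised SAP itself reports, and that variation can appear as subgroup effect modification. It would go too far to say that it does: this depends on race and ethnicity shares by site, which the documents do not give.

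Under the graded mixes the false-positive rate is about 6–26% with the highest minority share at the reversed site, about 6–12% averaged over orderings, and nominal with equal mix. A sharper contrast between the reversed site and the rest gives more, as Run B shows. These figures assume the planned sample sizes, true site heterogeneity about as large as estimated, a binary race variable and no time term. If the true heterogeneity is smaller, the bias shrinks with it. Adding site-by-period terms removes it in every setting tried.

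**What to change.** For the effectiveness outcome, fit the race-by-period and ethnicity-by-period models with site-by-period terms added (3 df). At minimum, report this as a sensitivity analysis beside Table 28 and the forest plot. State which model produced Table 28. Add a table of race and ethnicity by site and period; if the mix at the reversed site is close to that elsewhere, the concern falls away.

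For the implementation outcome, assess site-by-period before saying anything similar about Table 19. Do not use fixed site-by-period terms where a site-arm is all zeros: that site's period log-OR is then not estimable, and under ChangeToOne it would rest on one artificial event. Leave Tables 17, 18, 26 and 27 as they are.

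The cost is three parameters, one table from data already held, and subgroup standard errors about 2–20% larger, with the largest increase where the bias is largest.
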